7.3 MEDICAL HISTORY

Medical history will be coded using MedDRA dictionary. A medical history listing will be presented.

8.0 PRIOR AND CONCOMITANT MEDICATIONS

All medications recorded on the CRFs will be coded using the WHO DRUG Dictionary Enhanced September 2018. Prior and concomitant medications will be summarized by treatment arm in the safety population by anatomical therapeutic chemical (ATC) Class Level 4 and WHO Drug base substance preferred name.

Prior medications are defined as medications with stop dates occurring before the date of first administration of any study treatment component. Concomitant medications are defined as medications with start dates occurring on or after the date of first administration of any study treatment component and no more than 7 days after the last administration of any study treatment component. Medications with start and stop dates that bracket the date of first administration of any study treatment component will be summarized as both prior and concomitant medications.

Medications that were clearly stopped prior to the date of first administration of any study treatment component will be included in the prior medications table, and medications that clearly started on or after the date of first administration of any study treatment component will be included in the concomitant medications table. All other medications will be included in both the prior and concomitant medications tables.

Prior and Concomitant medication will be summarized for the safety population.

9.0 EFFICACY ANALYSES

The number of partial and complete cataplexy attacks, as well as the total number of attacks, are recorded daily. In addition, the rating of the ability to concentrate (1=Very Good, 2=Good, 3=Average, 4=Poor, 5=Very Poor) and the total number of inadvertent naps or sleep attacks are recorded daily. Unless otherwise stated, for these daily captured efficacy variables, the weekly average will be used in the analyses. The weekly average is derived by the average of the non-missing scores captured during the 7 days prior to the given visit. For example, the baseline score will be derived by the average of the non-missing scores captured during the 7 days prior to randomization date.

9.1 PRIMARY EFFICACY VARIABLE

9.1.1 DERIVATION OF PRIMARY EFFICACY VARIABLE

Primary Efficacy Variable

The primary efficacy variable will be the change from baseline in the total number of cataplexy attacks. The change will be calculated as Baseline – Post Baseline. A positive change is indicative of improvement.

9.1.2 PRIMARY ANALYSIS

The changes from baseline in the total number of cataplexy attacks will be analyzed using a Mixed Model. This model will include Sequence (1 or 2), patient, treatment (AXS-12 or placebo), Period as fixed effects and intercept as random. [REDACTED]

[REDACTED]

The estimated treatment effects as well as the treatment differences (AXS-12 - Placebo) along with the 95% confidence intervals of the treatment differences will be presented.

The primary endpoint or timepoint will be the overall treatment difference, then Week 2 of the treatment, followed by Week 1 of treatment.

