1.0 DOCUMENT HISTORY

Version	Date	Changes made since previous version
1.00	4 Nov 2019	Original
1.01	12 Nov 2019	Section 9.1 – Corrected typographical errors.

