3.0 INTRODUCTION

This statistical analysis plan (SAP) is based on [Protocol AXS-12-201, Amendment 2](#), dated 25 Apr 2019.

The purpose of this document is to provide details on study populations and on how the variables will be derived, how missing data will be handled, as well as details on statistical methodologies to be used to analyze the safety and efficacy data from the study.

The document may evolve over time, for example, to reflect the requirements of protocol amendments or regulatory requests. However, the final SAP must be finalized, approved by the Sponsor, and placed on file before the database is locked and treatment codes are unblinded. The approved plan will be used to carry out all analyses for the clinical study report. Deviations, if any, from the approved plan will be noted in the clinical study report.

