6.2 SOFTWARE

6.3 CHANGES TO PLANNED ANALYSES

Draft versions of the SAP will be numbered sequentially as Version 0.0i. The final approved version will be numbered as Version 1.00. Revisions after the “Final” version will be numbered as Version 1.0x. The Clinical Study Report will document any changes made after the final version approved before unblinding.

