9.4 ADJUSTMENTS FOR MULTIPLICITY

This study has one primary efficacy endpoint. Other than the primary endpoint, the purpose of the study with a small sample size is to generate hypotheses rather than to prove hypotheses. No p-value adjustment will be made in hypothesis testing.

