| 
STUDY DURATION
 | 
The duration of participation will be approximately 9 weeks as follows: Screening Period: up to 21 days Treatment Period 1: 3 weeks, including one week of down titration Treatment Period 2: 3 weeks, including one week of down titration
 |

| | |
|----------------------------------|---|
| 
CRITERIA FOR EVALUATION
 | 
Primary Efficacy Variable: The primary efficacy variable is the frequency of cataplexy attacks as self-reported in the Sleep and Symptom Daily Diary
 
Primary Endpoint: The primary efficacy endpoint is the change from Baseline to Week 2 of each treatment period in the frequency of cataplexy attacks as recorded in the Sleep and Symptom Daily Diary. Baseline will be calculated as the mean number of attacks during the 7 days prior to the study visit.
 
[REDACTED]
 
Secondary Efficacy Variables: Secondary efficacy variables will include:
 
• PGI-C• HAM-D• ESS• NSAQ• Ability to Concentrate item of the NSAQ• Safety variables: reports of treatment-emergent adverse events (TEAEs); clinical laboratory test results; vital sign measurements; and physical examination findings. |
| 
STATISTICAL METHODS
 | 
Analysis Populations: The following analysis populations are planned for this study:
 
• Modified Intent-to-Treat (mITT) Population: the mITT is the primary analysis population and will include data from all subjects who receive at least one dose of study medication and provide at least 1 post-dose efficacy assessment.• Safety Population: The Safety Population will include all subjects who receive at least 1 dose of the study medication. 
Membership in the analysis populations will be determined before unblinding.
 
The primary efficacy endpoint will be the change from Baseline to Week 2 of each treatment period in the number of cataplexy attacks as recorded in the Sleep and Symptom Daily Diary. Details of the statistical analysis will be provided in a Statistical Analysis Plan.
 |
| 
SAMPLE SIZE DETERMINATION
 | 
A sample size of 20 subjects was selected based on analysis of published results from a pilot open-label trial of reboxetine in narcoleptic subjects, and analyses of treatment effects of other agents studied in cataplexy.
 |

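### The protocol makes Week 2 the primary endpoint, the SAP ranks an 'overall' difference above it, and no visible text records the change

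*SAP*

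**What the plan says.** The protocol synopsis fixes the timepoint in two places. Under Criteria for Evaluation: "The primary efficacy endpoint is the change from Baseline to Week 2 of each treatment period in the frequency of cataplexy attacks". Under Statistical Methods: "The primary efficacy endpoint will be the change from Baseline to Week 2 of each treatment period in the number of cataplexy attacks". Only after that second statement does it leave the details of the analysis to the SAP.

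SAP 9.1.2 gives a different order: "The primary endpoint or timepoint will be the overall treatment difference, then Week 2 of the treatment, followed by Week 1 of treatment". SAP 9.4 says "This study has one primary efficacy endpoint" and continues: "Other than the primary endpoint, the purpose of the study with a small sample size is to generate hypotheses rather than to prove hypotheses". SAP section 6.0 sets the level at two-sided 0.05.

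SAP 3.0 gives the SAP control of the report: "The approved plan will be used to carry out all analyses for the clinical study report". It bases the SAP on protocol Amendment 2 of 25 April 2019.

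**The concern.** Week 2 is the sole primary endpoint in the protocol and comes second in the SAP. Because SAP 9.4 allows one primary endpoint, the natural reading is that 'overall' has taken its place. This is the only test the plan exempts from the hypothesis-generating label, so it decides whether the trial is called positive. If the 'overall' and Week 2 results fall on opposite sides of 0.05, the trial succeeds under one document and fails under the other.

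The visible reporting rules would not bring the switch to light. SAP 3.0 has the study report note deviations from the approved SAP, and SAP 6.3 covers changes made after the final SAP. This change lies between the protocol and the SAP, so neither rule reaches it.

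**Working it through.** **1. The endpoint statements side by side**

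| Place | Timepoint of the primary endpoint |
|---|---|
| Protocol synopsis, Criteria for Evaluation | Week 2 of each period |
| Protocol synopsis, Statistical Methods | Week 2 of each period |
| Protocol synopsis, Study Design | none named |
| SAP 4.3 | none named |
| SAP 9.1.1 | none named |
| SAP 9.1.2 | 'overall' first, Week 2 second, Week 1 third |

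The statements that name no week fit either version, so they do not settle the matter.

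**2. Where a change would be recorded**

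- SAP 6.3 carries the right title, but its visible text gives version-numbering rules and one reporting rule: "The Clinical Study Report will document any changes made after the final version approved before unblinding". It lists no departure from the protocol.
- SAP 1.0 describes the only revision to Section 9.1 as "Corrected typographical errors".

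**3. How often the two tests could disagree (illustration)**

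The plan has no figure to reproduce: SAP 9.5 gives 20 subjects without effect, SD or power.

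- From the documents: 20 subjects, 1:1 to two sequences, two-sided 0.05. With two sequences of 10 the error df is 20 − 2 = 18.
- Assumed: 'overall' is the mean of Weeks 1 and 2; equal weekly variances; between-week correlation r from 0.3 to 0.9; Week 1 effect e = 0.667 or 1 times the Week 2 effect; Week 2 power 50%, 80% or 95%. The value 0.667 is borrowed from the placebo capsule counts in the synopsis (2 a day in Week 1, 3 in Week 2).

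The noncentral t with 18 df gives Week 2 noncentrality of 2.071, 2.963 and 3.815 for 50%, 80% and 95% power. For the mean of two weeks,

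ncp(overall) = ncp(Week 2) × [(1 + e)/2] / √[(1 + r)/2].

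Two examples at 80% Week 2 power:

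- e = 1, r = 0.5: 2.963 × 1 / √0.75 = 3.42, so 'overall' has 89.9% power.
- e = 0.667, r = 0.9: 2.963 × 0.833 / √0.95 = 2.53, so 'overall' has 66.9% power.

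Simulated share of trials with opposite verdicts at 0.05 (400,000 trials per cell):

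| Week 2 power | e | r = 0.3 | r = 0.5 | r = 0.7 | r = 0.9 |
|---|---|---|---|---|---|
| 50% | 0.667 | 0.211 | 0.176 | 0.145 | 0.123 |
| 50% | 1 | 0.253 | 0.198 | 0.143 | 0.078 |
| 80% | 0.667 | 0.142 | 0.130 | 0.123 | 0.135 |
| 80% | 1 | 0.154 | 0.128 | 0.096 | 0.053 |
| 95% | 0.667 | 0.048 | 0.051 | 0.059 | 0.081 |
| 95% | 1 | 0.047 | 0.041 | 0.033 | 0.020 |

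Direction and power at 80% Week 2 power:

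| e | Quantity | r = 0.3 | r = 0.5 | r = 0.7 | r = 0.9 |
|---|---|---|---|---|---|
| 0.667 | only 'overall' significant | 0.084 | 0.049 | 0.020 | 0.001 |
| 0.667 | only Week 2 significant | 0.058 | 0.081 | 0.103 | 0.133 |
| 0.667 | power of 'overall' | 0.825 | 0.769 | 0.717 | 0.669 |
| 1 | only 'overall' significant | 0.144 | 0.113 | 0.078 | 0.037 |
| 1 | only Week 2 significant | 0.010 | 0.015 | 0.019 | 0.017 |
| 1 | power of 'overall' | 0.935 | 0.899 | 0.859 | 0.820 |

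The two parts agree: at e = 1 and r = 0.3 the simulated difference 0.144 − 0.010 = 0.134 matches the power difference 0.935 − 0.80 = 0.135.

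**The case against.** - **Redaction.** Text is blacked out in SAP 9.1.2 and directly after the primary endpoint in the synopsis. It may define 'overall', give a testing rule or offer a reason, and none of these is counted as missing. It cannot undo a visible sentence that ranks Week 2 second or a protocol that names Week 2 twice.
- **Version.** Only a synopsis is supplied, with no visible version. SAP 4.3 follows its design text closely but drops two secondary measures (MWT and PGI-S), so the SAP may rest on different protocol text. This stands as a limit: the match to Amendment 2 must be confirmed.
- **Delegation to the SAP.** The protocol defers analysis details only after it has fixed the endpoint, so this does not explain a different timepoint.
- **Weak silence.** The document history logs changes between SAP versions, so a difference already in version 1.00 would not appear there. That is fair. SAP 6.3 remains the natural place, and nothing is visible there.
- **Low stakes.** The trial is a small proof of concept, the SAP is to be final before unblinding, and Week 2 would probably still be reported. This answers any charge of choosing after the fact, and none is made. It does not say which test decides the trial.
- **Soft numbers.** The 0.667 floor assumes that effect follows capsule count, which no text supports. A smaller Week 1 effect would raise disagreement, to as much as 50%. With no Week 1 effect, 'overall' would have only about 30% to 41% power when Week 2 has 80%.

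**Conclusion.** The concern holds and should be settled before unblinding. The supplied protocol synopsis and SAP 9.1.2 name different primary tests, and no visible text records or explains the difference. This follows from the wording and needs no calculation.

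Under the stated assumptions, the two tests give opposite verdicts in about 2% to 25% of trials: 8% to 25% at 50% Week 2 power, 5% to 15% at 80% and 2% to 8% at 95%. At 80% Week 2 power the 'overall' test has 67% to 94% power, so neither choice is always better. A different make-up of 'overall' would move these figures, so they illustrate the stakes and are not bounds. If the SAP order is a fixed sequence, which is the natural reading, Type I error stays at 0.05, and no inflation is claimed.

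**What to change.** First confirm the primary endpoint in protocol Amendment 2. If it is Week 2, make the documents agree before unblinding in one of two ways. The choice is the sponsor's.

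(a) Replace the last sentence of SAP 9.1.2 with:

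> The single primary endpoint is the baseline-to-Week-2 change within each period (diary Days 8–14 and 29–35), tested two-sided at 0.05. The overall and Week 1 differences are supportive.

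(b) Keep 'overall' as primary and amend the protocol to match. If the redacted text does not already do so, state which diary days 'overall' covers, and that Week 2 and then Week 1 are tested only if the preceding test gives p < 0.05. This follows the order already in SAP 9.1.2.

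In either case, record the choice and its reason in SAP 6.3.

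The cost is low. Option (a) is one SAP sentence, plus any redacted text built around 'overall'. It gives up some power if the Week 1 effect is close to the Week 2 effect: 80% against 82% to 94% when the two are equal, under the assumptions above. Option (b) needs a protocol amendment.

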9.1.3 HANDLING OF MISSING VALUES

Missing values will not be imputed.

9.2 SECONDARY EFFICACY OUTCOMES

Secondary endpoints include:

- Changes from Baseline (Baseline – Post Baseline) in the total number of inadvertent naps or sleep attacks in the daily diary. [REDACTED]
- Changes from Baseline (Baseline – Post Baseline) in the rating of the ability to concentrate in the daily diary. [REDACTED]
- Patient Global Impression of Change (PGI-C) for cataplexy. [REDACTED] The frequency counts of categories will also be presented.
- Changes from Baseline (Baseline – Post Baseline) in the Hamilton Depression Rating Scale (HAM-D). [REDACTED]
- Changes from Baseline (Baseline – Post Baseline) in the Epworth Sleepiness Scale (ESS) score. [REDACTED]
- Narcolepsy Symptom Assessment Questionnaire (NSAQ).
 - Number of cataplexy attacks, Number of hypnagogic hallucinations, Number of sleep paralysis episodes, Number of inadvertent naps or sleep attacks during the day, Number of awakenings at night, Severity of daytime sleepiness: [REDACTED]

- “Quality of sleep at night”, “Ability to concentrate”, and “Overall, compared to my condition prior to starting on this experimental medicine, I am presently”:

9.3 INTERIM ANALYSES

No interim analyses are planned.

9.4 ADJUSTMENTS FOR MULTIPLICITY

This study has one primary efficacy endpoint. Other than the primary endpoint, the purpose of the study with a small sample size is to generate hypotheses rather than to prove hypotheses. No p-value adjustment will be made in hypothesis testing.

9.5 POWER AND SAMPLE SIZE JUSTIFICATION

A sample size of 20 subjects was selected based on analysis of published results from a pilot open-label trial of reboxetine in narcoleptic subjects, and analyses of treatment effects of other agents studied in cataplexy.

10.0 SUMMARIES OF MEASURES OF SAFETY

Safety analyses will be performed for the safety population. Safety evaluations will be based on the incidence, severity, relatedness, and type of adverse events, as well as on clinically significant changes in the subject’s physical examination, vital signs, and clinical laboratory results. Since patients received both treatments, the AEs will be attributed to the treatment they last received.

Because there is no pre-specified safety outcome defined in terms of AEs, clinically relevant laboratory parameters, or vital signs, any formal comparisons between the treatment arms with respect to specific safety parameters will be post-hoc.

10.1 EXTENT OF EXPOSURE

Summary statistics of exposure to study drug will be tabulated by treatment group, and by duration (in days) of exposure. The duration will be calculated as last dosing date – first dosing date + 1.

10.2 ADVERSE EVENTS

Each AE and serious adverse event (SAE) term recorded on the case report forms (CRFs) by primary system organ class (SOC) will be mapped to a preferred term using the MedDRA dictionary. The investigator will assess AE severity and relationship to the study treatment.

A treatment emergent adverse event (TEAE) is defined as any AE that occurs within the TEAE window. This window starts on the randomization date and ends 7 days after the last dosing date for non-serious AEs and 30 days after the last dosing for SAEs. All AEs that are considered by the Investigator as treatment related will be treated as TEAEs. Only TEAEs will be summarized in tables (unless otherwise stated AEs in tables are TEAEs). However, all AEs recorded will be listed. For the purpose of calculating treatment emergence and inclusion in summary tables, incomplete onset dates will be imputed as detailed in [Appendix B](#).

AEs will be summarized by the number and percent of subjects in each primary SOC and preferred term. Patients will be counted only once for each primary SOC and each preferred term. Summary tables of AEs by primary SOC, preferred term and severity will be provided. If a subject has more than one AE coded to the same preferred term, the subject will be counted only once for that preferred term by using the event with the highest severity. Similarly, if a subject has more than one AE within a primary SOC category, the subject will be counted only once in that SOC category by using the event with the highest severity. AEs by primary SOC, preferred term and relationship to study drug will be provided as well. If a subject has more than one AE coded to the same preferred term, the subject will be counted only once for that preferred term by using the most related event. Similarly, if a subject has more than one AE within a primary SOC category, the subject will be counted only once in that primary SOC category by using the most related event. In addition, SAEs by primary SOC and preferred term will be provided. Deaths and SAEs will be summarized similarly to AEs. All adverse event tables will also include the total number of events, counting multiple events per patient.

In the AE summary, preferred terms within each SOC will appear in alphabetical order.

Frequencies for deaths and hospitalizations will also be summarized by treatment group and overall.

Other safety analyses will be performed as appropriate

10.3 VITAL SIGNS

Vital signs, including blood pressure, heart rate, respiratory rate, and oral body temperature, will be measured after the subject has been in a seated position for at least 5 minutes. Vital sign values will be summarized by sequence and period.

10.4 PHYSICAL EXAM

Number and percent of subjects with abnormal physical exam findings at Screening will be summarized by body system, sequence and overall. Physical Exam data for each subject will also be presented in a listing.

11.0 IDENTIFICATION AND SUMMARY OF PROTOCOL DEVIATIONS

Major protocol deviations from entry criteria and treatment compliance will be summarized as far as they can be extracted from numeric or coded study data.

12.0 DATA QUALITY ASSURANCE

Accurate and reliable data collection will be ensured by verification and crosscheck of the CRFs against the investigator's records by the study monitor (source document verification) and by the maintenance of a drug-dispensing log by the investigator. Collected data will be entered into a computer database and subject to electronic and manual quality assurance procedures.

14.0 APPENDICES

14.1 APPENDIX A - LIST OF TABLES, LISTINGS, AND FIGURES

List of Tables, Figures, and Listings will be documented separately.

14.2 APPENDIX B - IMPUTATION ALGORITHM FOR PARTIAL AND MISSING DATES

This section describes missing date imputation methods.

For Adverse Events

If onset date is completely missing, onset date is set to date of randomization.

If (year is present and month and day are missing) or (year and day are present and month is missing):

- If year = year of randomization, then set month and day to month and day of randomization
- If year < year of randomization, then set month and day to December 31.
- If year > year of randomization, then set month and day to January 1.

If month and year are present and day is missing:

- If year=year of randomization and
 - If month = month of randomization then set day to day of first dose
 - If month < month of first dose then set day to last day of month
 - If month > month of first dose then set day to first day of month
- If year < year of randomization then set day to last day of month
- If year > year of randomization then set day to first day of month

For all other cases, set onset date to date of randomization.

For Concomitant Medications

Start Date: If start date is completely missing and end date is not prior to randomization, then the medication will be classified as concomitant. If start date is completely missing and end date is prior to randomization, then the medication will be classified as prior.

If (year is present and month and day are missing) or (year and day are present and month is missing) then set month and day to January 1. If year and month are present and day is missing then set day to first day of month.

End Date: If end date is completely missing then the medication will be classified as concomitant.

If (year is present and month and day are missing) or (year and day are present and month is missing) then set month and day to December 31. If year and month are present and day is missing then set day to last day of the month.

Note: that if both start and end dates are missing then the medication will be classified as concomitant.

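### Appendix B has no Period 2 anchor, and the SAP does not say how an adverse event with an incomplete onset date is assigned to a crossover period

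*SAP*

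**What the plan says.** Three parts of the SAP bear on this.

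- **Attribution (10.0).** "Since patients received both treatments, the AEs will be attributed to the treatment they last received". No reference date is given. The same section says that "any formal comparisons between the treatment arms with respect to specific safety parameters will be post-hoc".
- **Use of imputed dates (10.2).** "For the purpose of calculating treatment emergence and inclusion in summary tables, incomplete onset dates will be imputed". Assignment to a period or treatment is not among the stated uses. There is one treatment-emergent window for the whole study: it opens at randomization and "ends 7 days after the last dosing date for non-serious AEs and 30 days after the last dosing for SAEs". The section adds: "However, all AEs recorded will be listed".
- **The imputation rules (Appendix B).** With nothing known: "If onset date is completely missing, onset date is set to date of randomization". With the month missing: "If year = year of randomization, then set month and day to month and day of randomization". With only the day missing: "If month = month of randomization then set day to day of first dose"; a later month goes to its first day. Cases not covered go to randomization.

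The Treatment Regimens in the protocol synopsis put the start of Period 2 at Day 22 and the last planned dose at Day 38. SAP 4.3 schedules visits on Days 15, 22, 36 and 42.

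**The concern.** The Appendix B rules suit a parallel-group trial, where the only question is whether an AE began before or after treatment started. Pulling a doubtful onset towards the first dose is then cautious. A crossover asks a second question, namely under which treatment the AE began, and for that the same rules err in one direction.

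A programmer who has to place an AE in the AXS-12 or placebo column has one onset date available for an incomplete record, the imputed one. Using it with the rule in 10.0 sends Period 2 AEs to the Period 1 treatment, which is always the other treatment. A programmer who uses other information could produce a different table, and the SAP does not say which is intended. At stake is the by-treatment AE summary. Treatment emergence and the efficacy analyses are not affected.

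**Working it through.** The plan gives no figure to reproduce, so the check applies the Appendix B rules as written.

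**Inputs.** Period 2 starts on Day 22 and the last dose is on Day 38 (protocol synopsis). The window therefore ends on Day 38 + 7 = Day 45 for non-serious AEs and Day 38 + 30 = Day 68 for serious AEs (SAP 10.2). Assumed: first dose on the randomization date, onset uniform over days, and all 365 randomization dates of 2019 as an illustrative calendar.

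**One case.** A subject randomized on 15 May 2019 reaches Day 22 on 5 June. An onset recorded as June 2019 with the day missing is set to 1 June, which is Day 18 and so in Period 1. Yet 21 of that subject's 25 study days in June (Days 18 to 42) lie in Period 2. The result also turns on the calendar. For randomization on 10 June, 1 July is Day 22 (Period 2); for 11 June it is Day 21 (Period 1).

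**Share of Period 2 onsets imputed before Day 22:**

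| Missing part | to Day 42 | to Day 45 | to Day 68 |
|---|---|---|---|
| Day | 4,893/7,665 = 63.8% | 5,160/8,760 = 58.9% | 5,373/17,155 = 31.3% |
| Month | 7,434/7,665 = 97.0% | 8,460/8,760 = 96.6% | 16,027/17,155 = 93.4% |
| Whole date | 100% | 100% | 100% |

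**Reverse moves: 0.** For an onset on or after randomization, every branch returns a date no later than the true onset, so an AE can only move earlier.

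**Effect on the contrast.** Let A and P be the AE risks on AXS-12 and placebo, f the share of incomplete dates, s the share moved, and q = f × s. Take 1:1 sequences, equal missingness and independent events within a subject.

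- Sequence 1 (AXS-12 first): AXS-12 column A + qP(1 − A); placebo column P(1 − q).
- Sequence 2 (placebo first): AXS-12 column A(1 − q); placebo column P + qA(1 − P).
- Averaging the two differences, the cross terms cancel and leave (A − P)(1 − q).

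With assumed A = 40% and P = 20%, the true difference is 20 points:

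| Case | f = 2% | f = 10% | f = 30% |
|---|---|---|---|
| Day missing, to Day 42 (s = 0.638) | 19.7 | 18.7 | 16.2 |
| Day missing, to Day 68 (s = 0.313) | 19.9 | 19.4 | 18.1 |
| Whole date missing (s = 1) | 19.6 | 18.0 | 14.0 |

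In 20 subjects the true difference is 20 × 0.20 = 4.0 subjects. At f = 10% it becomes 3.7, 3.9 or 3.6, a loss of at most 0.4. At f = 30% with whole dates missing it becomes 20 × 0.14 = 2.8, a loss of 1.2.

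**The case against.** The strongest reply is that the SAP never links the imputed date to attribution. Section 10.2 names treatment emergence and inclusion in tables, and the anchors work for those. Attribution has its own rule in 10.0. Only the protocol synopsis is available, so the case report form or the protocol's AE section may already record AEs by visit or period. This stands: a reader might infer that the plan prescribes misattribution, and the documents do not say so. What remains is that the SAP gives no rule for these AEs and offers only an onset date that misplaces them.

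Three other inferences go too far.

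- *Every moved AE pulls the contrast towards zero.* In Sequence 1 a moved Period 2 placebo AE is added to AXS-12 and widens the contrast. Shrinkage holds only on average. About 20 × (0.40 + 0.20)/2 = 6 subjects would have a Period 2 AE, so at 10% day missing about 6 × 0.10 × 0.638 = 0.4 AEs move in the whole trial. The direction in this one trial cannot be predicted.
- *The month never settles the period.* That is true of the day-missing onsets that move. Over Days 1 to 42, 9,786/15,330 = 63.8% of day-missing onsets fall in a month shared by both periods; for the other 36.2% the month is enough.
- *Section 10.0 assigns every AE to the final treatment of the study.* The words could be read so, but the stated reason, that patients receive both treatments, points to the treatment most recent at the time of the AE. The wording needs a reference date; it is not evidence of that intention.

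It is also fair that the tables are descriptive and that the full listing lets a shift be traced.

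**Conclusion.** The gap is real and minor. If the imputed date is used for attribution, the error runs in one direction in time, from Period 2 to Period 1. With 1:1 sequences, equal missingness and a higher AE risk on AXS-12, it weakens the AE contrast on average. At an assumed 10% incomplete dates and the assumed risks above, the loss is under half a subject. It exceeds one subject only in an extreme case such as 30% of dates wholly missing. The documents give neither the rate of incomplete dates nor the AE risks, so these sizes are illustrative. The shares moved rest on uniform onset and on first dose at randomization.

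**What to change.** Keep the randomization anchor for treatment emergence. For attribution, add a short rule:

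1. Assign the period from the known date parts, the AE stop date and, where recorded, the visit of first report; the Day 22 visit separates the periods. Do not use the Appendix B imputed date.
2. Flag in the listing any AE whose period stays ambiguous and report the number of such AEs separately, without defaulting them to one treatment.
3. In 10.0, refer to the treatment most recently received before AE onset.
4. In Appendix B, use one anchor throughout the month comparison, which now mixes randomization and first dose.

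Counting ambiguous AEs under AXS-12 may look cautious but can distort more than the present rules. If nothing resolves them, the AXS-12 column is A + qP(1 − A) and the placebo column P(1 − q). The difference is then 0.20 + 0.32q, against an average shrinkage of 0.20q now. At 10% day missing that gives 22.0 points, and at 30% of dates wholly missing 29.6, where the true value is 20.

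The cost is a few sentences in the SAP and slightly more derivation work, with no new data to collect.
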